## **2.2 Rationale for the study design**

This is a phase II, double-blind, placebo controlled, multicenter study conducted in China. This study design is well-established to assess the efficacy and safety of everolimus/exemestane combination.

## **2.3 Rationale for dose and regimen selection**

The selection of the 10 mg continuous daily dose for everolimus is based on a pharmacodynamic model (Tanaka et al 2008), which was supported by results of a clinical pharmacodynamic study in patients with solid tumors (Tabernero et al 2008). The 10 mg daily dose of everolimus was favored over a 5 mg daily dose in Study C2108, a Phase I study combining everolimus with letrozole in postmenopausal patients with advanced breast cancer (Awada et al 2008). Everolimus 10 mg/day was effectively used as monotherapy in patients with recurrent/metastatic breast cancer (Ellard et al 2009). The same dose of everolimus showed positive efficacy outcomes in combination with letrozole as neoadjuvant therapy in patients with ER+ early breast cancer and in combination with tamoxifen in patient with ABC (Baselga 2009, Bachelot 2012). This was further corroborated by results from BOLERO-2 study, where a daily regimen of 10 mg everolimus in combination with exemestane 25 mg daily was more efficacious than exemestane alone (Piccart et al 2012).

The recommended daily dose of exemestane is 25 mg via oral administration.

[figure not shown]
## **2.4 Rationale for choice of combination drugs**

Results in BOLERO-2 study demonstrated PFS benefit of the combination of everolimus and exemestane compared to exemestane alone in postmenopausal women with HR+ HER2-, ABC who has a recurrence or progression on NSAI with acceptable safety profile (Yardley et

al 2013). The approved doses in the treatment of postmenopausal women with HR+ HER2- and ABC are 10 mg daily of everolimus plus 25 mg daily of exemestane via oral administration.

## 2.5 Risks and benefits

The risk to subjects in this trial may be minimized by compliance with the eligibility criteria and study procedures, close clinical monitoring, and dose modification, early termination procedure. There may be unforeseen risks with study treatment which could be serious.

### 3 Objectives and endpoints

**Table 3-1 Objectives and related endpoints**

Objective	Endpoint	Analysis
Primary		Refer to Section 10.4 .
To assess the combination treatment of everolimus and exemestane to exemestane and placebo with respect to progression-free survival	PFS, defined as the time from the date of randomization to the date of the first documented progression (as assessed by local assessment per RECIST 1.1) or death due to any cause	
Secondary		Refer to Section 10.5 .
To assess the two treatment arms with respect to PFS as determined by a Blinded Independent Review Committee (BIRC).	PFS, defined as the time from the date of randomization to the date of the first documented progression (as assessed by BIRC assessment per RECIST 1.1) or death due to any cause	
To assess the two treatment arms with respect to overall survival	OS, defined as time from date of randomization to date of death due to any cause	
To assess the two treatment arms with respect to following based on local investigator assessment and BIRC	The following endpoints will be evaluated by Investigator and BIRC assessment per RECIST 1.1: 
 
• Overall response rate (ORR)
 
• Clinical benefit rate (CBR)
 
• To summarize time to response and duration of response in the two treatment arms
 
	
Time to deterioration of ECOG Performance Status	ECOG PS categories are defined in Section 7.2.2 .	
To characterize the safety and tolerability of everolimus and exemestane versus placebo and exemestane in all patients	Adverse events (AEs), ECGs and laboratory abnormalities	

Objective	Endpoint	Analysis
Characterize the pharmacokinetics of everolimus (Cmin, C2h) when administered in combination with exemestane		
Compare the two treatment arms with respect to pre-dose concentration (Cmin) and concentration at 2 hours post dose (C2h) of exemestane and to compare the two treatment arms with respect to estradiol (E2) changes from baseline.		

## 4 Study design

### 4.1 Description of study design

This is a multicenter, double-blind, randomized, placebo-controlled, phase II study evaluating treatment with everolimus (10 mg daily) versus placebo in combination with exemestane (25 mg daily) in Chinese postmenopausal women with locally advanced, recurrent or metastatic ER positive HER2-negative breast cancer refractory to non-steroidal aromatase inhibitors.

Approximately 160 patients will be randomized in 1:1 ratio to receive either everolimus or matching placebo in a blinded manner in addition to open label exemestane (25 mg daily tablets).

#### Screening phase

Written informed consent must be obtained before any study specific medical procedures are performed. The investigator or his/her authorized designee will assign a unique number (subject number) to patients being considered for the study. Once assigned, the subject numbers for patients will not be reused.

The study will use Interactive Response Technology (IRT) for patient screening and management of everolimus drug supply. Exemestane will be supplied locally by Novartis in accordance with the country regulations.

After the patient signs the informed consent and prior to the first dose of study treatment, patients will be screened in IRT. All inclusion/exclusion criteria must be verified. Patients who do not meet the criteria will not be given the study treatment.

All screening assessments to confirm eligibility must be performed within maximum 21 days prior to the first dose of study treatment ([Table 7-1](#) and [Section 7.1](#)).

#### Screening for hepatitis B

During the screening phase, all patients should be tested for hepatitis B viral load and serologic markers of HBV-DNA, HBsAg, HBsAb, and HBcAb.

Patients with positive hepatitis B results should start prophylactic antiviral treatment of 1 to 2 weeks prior to the first doses of the study treatment, and should continue for at least 4 weeks after last dose of study treatment.

The management guidelines, in [Section 6.3.2.3](#), are provided according to the results of the baseline assessment of viral load and serological markers for hepatitis B.

#### Screening for hepatitis C

Patients with any of the following risk factors for hepatitis C should be tested using quantitative RNA-PCR

- known or suspected past hepatitis C infection (including patients with past interferon 'curative' treatment),
- blood transfusions prior to 1990,
- current or prior IV drug users,
- current or prior dialysis,
- household contact of hepatitis C infected patient(s),
- current or prior high-risk sexual activity,
- body piercing or tattoos,

At the discretion of the investigator, additional patients may also be tested for hepatitis C. The management guidelines, in [Section 6.3.2.3](#), are provided according to the results of the baseline assessment of hepatitis C viral load.

#### **Randomized treatment phase**

All eligible patients will be randomized within 7 days before Cycle 1 Day 1 to one of the two treatment arms: everolimus plus exemestane arm or placebo plus exemestane arm. Randomization will be stratified according to the presence of visceral disease and sensitivity to prior hormonal therapy status. Visceral refers to lung, liver, brain, pleural and peritoneal involvement. Sensitivity to prior hormonal therapy is defined as either (1) documented clinical benefit (complete response, partial response, stable disease  $\geq$  24 weeks) to at least one prior hormonal therapy in the advanced setting or (2) at least 24 months of adjuvant hormonal therapy prior to recurrence.

Randomized patients will start the study treatment at Cycle 1 Day 1. Patients will receive everolimus/placebo (10 mg daily oral tablets) in addition to exemestane (25 mg daily oral tablets) continuously. Dose adjustment (reduction, interruption) according to safety findings will be allowed ([Section 6.3](#)).

Patients will receive treatment until disease progression (assessed by RECIST 1.1), unacceptable toxicity, death or discontinuation from treatment for any other reason. Tumor assessments will be performed every 8 weeks after randomization until radiological progression per local assessment. Tumor assessments are to be performed every 12 weeks after data cut-off for primary analysis and as clinically indicated, until disease progression.

Imaging data used for tumor assessments during treatment phase and follow-up phase will be centrally collected, checked for quality and reviewed by a central vendor designated by

Novartis. The central review of the scans will be carried out in a blinded fashion. The decision regarding patient management will remain with the local investigator.

### **Post-treatment follow-up phase**

After end of treatment visit, all patients will be followed up for safety up to 30 days after last dose of study treatment (exemestane and/or everolimus/placebo).

All patients who discontinue from study treatment due to disease progression must have their progression clearly documented according to the criteria specified in RECIST 1.1.

[figure not shown]
If a patient permanently discontinues study treatment for reasons other than disease progression, death, lost to follow-up, or withdrawal of consent to efficacy follow-up then tumor assessments should continue to be performed per assessment schedule until disease progression, death, lost to follow-up or withdrawal of consent for efficacy follow-up.

Antineoplastic therapy regimen received between EOT and progression will also be collected as well as the first regimen received after progression.

### **Survival follow-up phase**

All patients will be followed for survival status at least every 3 months after randomized treatment phase or post-treatment follow-up phase unless they discontinued due to death, consent withdrawal or lost to follow-up. Survival information can be obtained via phone and information will be documented in the source documents and eCRF. Additional survival assessments may be performed more frequently if a survival update is required for reporting the results or to meet safety or regulatory needs.

**Figure 4-1** Study design

## 4.2 Timing of interim analyses and design adaptations

Not applicable.

## 4.3 Definition of end of study

The primary analysis will occur when approximately 110 PFS events have been documented based on local assessment (refer to [Section 10.4](#)). At this time, the primary clinical study report (CSR) will be produced.

After the primary analysis of PFS, the study will remain open provided the PFS demonstrates treatment benefit. Patients still being followed on the study after the primary analysis time point will continue as per the schedule of assessments.

The end of study is defined as the earliest occurrence of one of the following:

- All patients have died or discontinued from the study
- Another clinical study or patient support programs becomes available that can continue to provide Afinitor in this patient population and all patients ongoing are eligible to be transferred to them
- Afinitor has been approved for this indication in combination with Exemestane

The final analysis of study data will be conducted at the end of the study. All available data from all patients up to this cutoff date will be analyzed.

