### **10.4.2 Statistical hypothesis, model, and method of analysis**

No hypothesis testing will be performed and the objective of this study is to estimate hazard ratio of everolimus in combination with exemestane compared to exemestane alone.

PFS as determined by local evaluation will be analyzed based on the data from FAS according to the treatment arm and randomization strata to which patients were assigned. The distribution of PFS will be estimated using the Kaplan-Meier method. The median PFS along with 90% CI will be presented by treatment arm. The Kaplan-Meier curves will be displayed and the number of patients at risk at certain time points will be shown on the plot.

A Cox regression model stratified by randomization stratification factors will be used to estimate the hazard ratio (HR) of PFS, along with 90% CI. As this is an estimation based approach, no p-value will be provided.

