## 10.6 Sample size calculation

As this is a bridging study for China registration, this study will pursue an estimation strategy rather than formal hypothesis testing.

Based on the results of RAD001Y2301 study, the median PFS for the exemestane arm was 4.1 months, and the everolimus plus exemestane arm improved median PFS in Asian patients by 38%. Assuming the same hazard ratio of 0.62 in Chinese patients, this will result in an increase in median PFS from 4.1 months to 6.6 months for the everolimus plus exemestane arm, under the exponential model.

If the observed hazard ratio is 0.62, the 90% CI of the hazard ratio based on a total of 110 PFS events will be (0.45, 0.85). Assuming enrolment will continue for approximately 18 months at a uniform rate, and about 10% of the patients will be lost to follow-up for PFS evaluation, approximately 160 patients will need to be randomized to the two treatment groups in 1:1 ratio to observe the 110 PFS events at approximately 22 months following the randomization of the first patient in this study.

Below table shows the 90% CIs for various observed hazard ratios.

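### Protocol 4.3 keeps the study open only if PFS shows an undefined treatment benefit, which could truncate overall survival follow-up after a neutral or adverse result

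*Protocol*

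**What the plan says.** Protocol 4.3 places the primary analysis at about 110 locally assessed PFS events and then says: "After the primary analysis of PFS, the study will remain open provided the PFS demonstrates treatment benefit". It adds that patients still in follow-up carry on with the assessment schedule. It then continues: "The end of study is defined as the earliest occurrence of one of the following". The list has three items: every patient has died or left the study; another study or support program can take over all ongoing patients; the combination is approved for this indication. None refers to the PFS result. SAP 2.1 repeats the three items without the condition.

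On what could count as benefit, Protocol 10.4.2 says: "No hypothesis testing will be performed and the objective of this study is to estimate hazard ratio of everolimus in combination with exemestane", and then: "As this is an estimation based approach, no p-value will be provided". Protocol 10.6 says that "this study will pursue an estimation strategy rather than formal hypothesis testing". SAP 2.5.2 takes the same line. No hazard ratio or confidence limit is named as a criterion.

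On survival, Protocol 4.1 (survival follow-up phase) and 7.1.6.3 follow all patients at least every 3 months unless they have died, withdrawn consent or been lost. The PFS result plays no part. OS is a secondary objective, and SAP 2.7 plans a single OS analysis at the end of the study.

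**The concern.** The condition in 4.3 is a results-dependent rule with no criterion and no named decision-maker. After a weak PFS result it points to closing the study, while the end-of-study list that follows it, SAP 2.1, and the survival sections 4.1 and 7.1.6.3 all point to continuing. Two people applying the protocol in good faith could act in opposite ways on the same data.

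What is at stake is the completeness and precision of OS. If the study closed at the primary analysis, survival follow-up would stop early in exactly the case where PFS was neutral or adverse. The length of OS follow-up would then depend on the PFS outcome. The protocol describes no independent body for the decision: there is no data monitoring committee (8.6), and the steering committee's data review is limited to blinded pooled safety data (8.7).

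**Working it through.** **The plan's own figure.** Protocol 10.6 gives 110 PFS events, 1:1 allocation and a 90% interval of 0.45 to 0.85 at an observed hazard ratio (HR) of 0.62.

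- SE(log HR) = 2/√110 = 0.1907.
- 90% limits = HR × exp(±1.645 × 0.1907).
- At 0.62 this gives 0.453 to 0.848; at 0.45, 0.329 to 0.616; at 0.84, 0.614 to 1.149. All three rows of Table 10-1 are reproduced.

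**How much the missing criterion matters.** Take log HR as normal around the log of the true HR with SE 0.1907. Two illustrative readings of benefit are used; neither is in the documents.

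- Reading A, upper 90% limit below 1: the observed HR must be below exp(−1.645 × 0.1907) = 0.731.
  - True HR 0.62: Φ[(ln 0.731 − ln 0.62)/0.1907] = Φ(0.86) = 0.806, so the condition fails with probability about 19%.
  - True HR 0.84: Φ(−0.73) = 0.233, so it fails with probability about 77%.
- Reading B, observed HR below 1.
  - True HR 0.62: Φ(0.478/0.1907) = Φ(2.51) = 0.994, failing about 0.6%.
  - True HR 0.84: Φ(0.174/0.1907) = Φ(0.91) = 0.82, failing about 18%.

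**What closure at the primary analysis would leave for OS.** Protocol 10.6 assumes 160 patients, uniform accrual over 18 months, and 110 events at about 22 months. Assume, for illustration, the OS medians of the earlier phase III trial quoted in Protocol 1.1.2 (26.55 months control, 30.98 months combination), exponential survival and no loss.

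- The expected proportion dead in an arm at month T is 1 − [exp(−λ(T−18)) − exp(−λT)]/(18λ), with λ = ln 2/median.
- At T = 22: control 0.281 × 80 = 22.5 deaths and combination 0.247 × 80 = 19.8, about 42 in total. Around that trial's OS HR of 0.89, the 90% interval is 0.89 × exp(±1.645 × 2/√42.3) = 0.54 to 1.48.
- At T = 46: about 94 deaths and an interval of 0.63 to 1.25.
- If the control median is varied from 20 to 35 months, with the combination median set at control/0.89, deaths at 22 months range from about 54 to 34.
- Protocol 10.5.1.2 plans survival proportions out to 18 months. At month 22 only patients randomized in the first 4 months, 160 × 4/18 ≈ 36, could have 18 months of follow-up.

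**The case against.** The strongest reply is that 4.3 contains no OS stopping rule. The sentence speaks of the study, the next one keeps patients on schedule, and 4.1 and 7.1.6.3 follow everyone for survival. The Amendment 1 log records that a sentence ending OS follow-up without PFS benefit was removed, which suggests that the sponsor meant to keep it. This stands in part: the effect on OS is inferred from study closure. But the retained sentence still closes the study if the condition fails, and nothing says that the survival sections override it.

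A reader might infer several stronger things that the documents do not support.

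- *That OS would not be followed at all after a weak PFS result.* Survival is collected from each patient's exit from treatment or post-treatment follow-up, so what had accrued by about 22 months would remain. OS would be truncated.
- *That an estimation-only trial cannot show benefit.* An estimated hazard ratio with its 90% interval can inform that judgement. What is missing is the criterion.
- *That an error rate is affected.* Nothing is tested, so none is. Any decision after a PFS comparison is also necessarily made with knowledge of the arms, so that alone is no fault.
- *That OS was lost in practice.* The SAP plans a final report with an OS analysis, written after the 19 May 2020 primary cut-off and the February 2022 approval. This does not indicate that the study closed at the primary analysis.

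It is also true that 4.4 lets the sponsor stop at any time and that approval is itself a listed end of study, so no edit to this sentence guarantees OS follow-up. A general termination right is still different from a pre-written rule tied to the PFS result.

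**Conclusion.** The point holds as an unreconciled and undefined condition with a real but bounded consequence. At the design hazard ratio of 0.62, the chance that the condition fails is about 0.6% or 19% under the two illustrative readings; at 0.84 it is about 18% or 77%. These rest on 110 events, a normal approximation for log HR and thresholds chosen here, so they show how far the action depends on the reading and do not estimate the chance of closure. If closure came at 22 months, OS would rest on about 42 deaths (34 to 54 over the medians tried), against about 94 with two more years, assuming exponential survival and no loss. The harm is to the completeness and precision of a secondary endpoint.

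**What to change.** Amend Protocol 4.3 so that the PFS condition does not apply to survival follow-up: all patients stay in it, whatever the PFS result, until a listed end-of-study event, subject to the sponsor's right in 4.4. Reconcile the sentence with the end-of-study list in 4.3, with 4.1 and 7.1.6.3, and with SAP 2.1. If the sponsor keeps a PFS condition for other activities, its criterion and decision-maker should be stated. Whether imaging and study treatment continue is left to the sponsor; deleting the condition outright would also keep the 12-weekly imaging open, so the narrower change is the cheaper one.

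The cost is a sentence or two of text and survival contacts every 3 months, which may be by phone, after a weak PFS result. Because the SAP was written after the primary cut-off, the final report should also say how continuation was decided and by whom.

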## 4.4 Early study termination

The study can be terminated at any time for any reason by Novartis. Should this be necessary, the patient will be contacted by the investigator or his/her designee. The patient should be seen as soon as possible for an end of treatment visit / or end of post treatment follow up visit and the same assessments should be performed as described in [Section 7](#) for a discontinued or withdrawn patient. The investigator may be informed of additional procedures to be followed in order to ensure that adequate consideration is given to the protection of the patient's interests. The investigator will be responsible for informing IRBs and/or ECs of the early termination of the trial.

# 5 Population

## 5.1 Patient population

Chinese Postmenopausal women with ER+ HER2- locally advanced, recurrent, or metastatic breast cancer after recurrence or progression on prior letrozole or anastrozole.

Patients enrolled in this study are not permitted to participate in additional parallel investigational drug or device studies. Patients who have discontinued this study won't be re-enrolled.

The investigator or designee must ensure that only patients who meet all the following inclusion and none of the exclusion criteria are offered treatment in the study.

## 5.2 Inclusion criteria

Patients eligible for inclusion in this study have to meet **all** of the following criteria:

1. Women (18 years or older) with locally advanced, recurrent, or metastatic breast cancer. Locally advanced breast cancer must not be amenable to curative treatment by surgery or radiotherapy.
2. Histological or cytological confirmation of estrogen-receptor positive (ER+) breast cancer
3. Postmenopausal women. Postmenopausal status is defined either by:
  - Prior bilateral oophorectomy
  - Or age  $\geq 60$
  - Or age  $< 60$  and amenorrhea for 12 or more months (in the absence of chemotherapy, tamoxifen, toremifene, or ovarian suppression), and FSH and estradiol in the postmenopausal range (serum FSH  $> 40$  mIU/mL and estradiol  $< 20$  pg/mL or according to the postmenopausal range defined by local laboratory).

For women with therapy-induced amenorrhea, oophorectomy or serial measurements of FSH and/or estradiol are needed to ensure postmenopausal status.

**Note:** Ovarian radiation or treatment with a luteinizing hormone-releasing hormone (LH- RH) agonist (goserelin acetate or leuprolide acetate) is not permitted for induction of ovarian suppression.

4. Recurrence or progression on prior NSAI is defined as:
  - Recurrence while on, or within one year (12 months) of end of adjuvant treatment with letrozole or anastrozole
  - or
  - Progression while on or within one month (30 days) of the end of prior treatment with letrozole or anastrozole

Notes:

- Letrozole or anastrozole do not have to be the last treatment prior to the enrollment in the study
- Patients must have improved to grade 1 or better from any adverse events (with exception of alopecia) related to previous therapy prior to enrollment
- 5. Radiological or objective evidence of recurrence or progression on or after the last systemic therapy prior to enrollment
- 6. Patients must have recovered to grade 1 from any adverse events (except alopecia) related to prior therapy prior to randomization.
- 7. Patient must have as per RECIST 1.1
  - measurable disease
  - or
  - non-measurable lytic or mixed (lytic + blastic) bone lesions in the absence of measurable disease.

**Note:** Measurable lesions include lytic or mixed (lytic + blastic) bone lesions, with an identifiable soft tissue component that meets the measurability criteria per RECIST 1.1.

Patients with only non-measurable lesions (e.g. pleural effusion, ascites) and no lytic or a mix of lytic and blastic bone lesions are not eligible.

8. Patient is able to swallow and retain oral medication
9. Patient must meet the following laboratory values at the screening visit:
  - Absolute Neutrophil Count (ANC)  $\geq 1.5 \times 10^9/L$
  - Platelets  $\geq 100 \times 10^9/L$
  - Hemoglobin (Hgb)  $\geq 9 \text{ g/dL}$
  - INR  $\leq 2$
  - Serum creatinine  $\leq 1.5 \times \text{ULN}$
  - Total bilirubin  $\leq 1.5 \times \text{ULN}$  ( $\leq 3 \times \text{ULN}$  for patients known to have Gilbert Syndrome)
  - Aspartate transaminase (AST)  $\leq 2.5 \times \text{ULN}$ , except for patients with liver metastasis, who may only be included if AST  $\leq 5.0 \times$
  - Alanine transaminase (ALT)  $\leq 2.5 \times \text{ULN}$ , except for patients with liver metastasis, who may only be included if ALT  $\leq 5.0 \times \text{ULN}$
  - Fasting serum cholesterol  $\leq 300 \text{ mg/dL}$  or  $7.75 \text{ mmol/L}$  and fasting triglycerides  $\leq 2.5 \times \text{ULN}$ . In case one or both of these thresholds are exceeded, the patient can only be included after initiation of statin therapy and when the above mentioned values have been achieved
10. Patient has a WHO performance status  $\leq 2$
11. Written informed consent must be obtained prior to any screening procedures.

